Clinical Performance Evaluation of Two Frequent
Replacement
Silicone Hydrogel Toric Contact Lenses

STUDY ID
CLN109-C001

[figure not shown]
STATISTICAL ANALYSIS PLAN

NCT05959200

Statistical Analysis Plan for CLN109-C001

**Title: Clinical Performance Evaluation of Two Frequent Replacement
Silicone Hydrogel Toric Contact Lenses**

This version of the Statistical Analysis Plan is based on Version 3.0 of the study protocol.

[figure not shown]
Executive Summary:

Key Objectives:

To evaluate the percentage of Alcon serafilcon A Toric (LID226397) contact lenses with axis orientation within ± 30 degrees from the 90° axis (ideal location), 10 minutes (min) after lens insertion at dispense visit.

Decision Criteria for Study Success:

Decision criteria for study success are not applicable for this study.

1 STUDY OBJECTIVES AND DESIGN

1.1 Study Objectives

PRIMARY OBJECTIVE

To evaluate the percentage of LID226397 contact lenses with axis orientation within ± 30 degrees from the 90° axis (ideal location), 10 min after lens insertion at dispense visit.

[figure not shown]
1.2 Study Description

Key components of the study are summarized in Table 1-1.

Table 1-1 Study Description Summary

[figure not shown]
| | |
|------------------|---|
| Study Design | Prospective, randomized [REDACTED], bilateral, crossover, controlled, double-masked, multicenter. |
| Study Population | Volunteer subjects aged 18 or over who are habitual soft toric contact lens wearers (excluding AOfAHP habitual lens wearers and habitual daily disposable lens wearers) with normal eyes (other than correction for refractive error). Subjects should have at least 3 months wearing experience, wear these lenses at least 5 days per week and at least 10 hours per day. |

| | |
|------------------------------|---|
| | Target to complete: 80 Planned to enroll: ~92 |
| Number of Sites | ~6 United States |
| Test Product(s) | Alcon serafilcon A toric contact lenses (serafilcon A; LID226397) |
| Comparator Product(s) | ACUVUE® OASYS for ASTIGMATISM with HYDRACLEAR® PLUS contact lenses (AOFAHP; senofilcon A) |
| Planned Duration of Exposure | ~ 28 days total duration (test and comparator): Test Product: 14 (-0/+2) days Comparator Product: 14 (-0/+2) days |
| Visits | Visit 1: Screening/Baseline/Trial fit Visit 2: Dispense Lens 1 [3 – 4* days after Visit 1] Visit 3: Week 1 Follow-up Lens 1 [7 -0/+ 1 days after Visit 2] Visit 4: Week 2 Follow-up Lens 1 [7 -0/+ 1 days after Visit 3] Visit 5: Dispense Lens 2 [2 (at least 48 hours) – 4* days after Visit 4] Visit 6: Week 1 Follow-up Lens 2 [7 -0/+ 1 days after Visit 5] Visit 7: Week 2 Follow-up Lens 2/ Exit [7 -0/+ 1 days after Visit 6] * Washout period with habitual spectacles only after Visit 1 and Visit 4 |

1.3 Randomization

A member of the Randomization Programming group at Alcon who is not part of the study team will generate the randomized allocation schedule(s) for study lens sequence assignment. Randomization will be implemented in the Electronic Data Capture (EDC)/randomization integration system.

Qualifying subjects will be randomized in a 1:1 ratio to receive treatment (lens) in one of the following crossover sequences:

- Sequence 1: LID226397/AOfAHP
- Sequence 2: AOfAHP/LID226397

1.4 Masking

This study is double-masked.

[REDACTED]

1.5 Interim Analysis

There are no plans to conduct an interim analysis and no criteria by which the study would be terminated early based upon statistical determination.

2 ANALYSIS SETS

2.1 Safety Analysis Set

Safety analyses will be conducted using the safety analysis set on a treatment-emergent basis. As such, the safety analysis set will include all subjects/eyes exposed to any study lenses evaluated in this study. [REDACTED]

[REDACTED]

For treatment-emergent safety analyses, subjects/eyes will be categorized under the actual study lenses exposed in the corresponding lens sequence.

2.2 Full Analysis Set

The full analysis set (FAS) is the set of all randomized subjects who are exposed to any study lenses evaluated in this study, except for lenses used for lens fitting at Visit 1.

2.3 Per Protocol Analysis Set

The per protocol (PP) analysis set is a subset of FAS and excludes all data/subjects that have met any of the critical deviation or evaluability criteria identified in the Deviations and Evaluability Plan (DEP).

3 SUBJECT CHARACTERISTICS AND STUDY CONDUCT SUMMARIES

The following tables will be presented:

- Subject Disposition by Lens Sequence
- Analysis Sets by Lens
- Analysis Sets by Lens Sequence
- Subject Accounting by Lens Sequence
- Demographics by Lens Sequence
- Baseline Characteristics by Lens Sequence [lens brand; ██████████
██████████ keratometry readings; C ██████████
██████████]

[figure not shown]
Subject accounting and demographics table will be summarized on the safety, full, and per protocol analysis datasets. Baseline characteristics will be summarized on the full and per protocol analysis datasets.

In addition, the following subject listings will be provided:

- Listing of Subjects Excluded from Protocol Defined Analysis Sets
- Listing of Lens Sequence Assignment by Investigator
- Listing of Subjects Discontinued from Study

[figure not shown]
4 EFFECTIVENESS ANALYSIS STRATEGY

This study defines 1 primary effectiveness ██████████
██████████ Effectiveness evaluations will use the FAS as the primary analysis set, except for endpoints relating to lens fitting, which will be summarized for all randomized subjects.

Continuous variables will be summarized using the number of observations, mean, standard deviation (SD), median, minimum, and maximum, as well as confidence intervals (CIs) or confidence limits where applicable. Categorical variables will be summarized with frequencies and percentages from each category.

All data obtained in evaluable subjects/eyes will be included in the analysis. No imputation for missing values will be carried out for the primary  effectiveness analyses.

[figure not shown]

[figure not shown]
A listing of select effectiveness data will also be provided.

[figure not shown]
4.1 Effectiveness Endpoints

Primary Effectiveness Endpoint

The primary effectiveness endpoint is the percentage of LID226397 contact lenses with axis orientation, recorded as deviations from 90° axis, between -30 degrees and +30 degrees, inclusive, assessed at the dispense visit, 10 min after lens insertion.

[figure not shown]

[figure not shown]

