## **5 INTRODUCTION**

### **5.1 Rationale and Background**

LID226397 contact lenses are indicated for the optical correction of refractive ametropia (myopia or hyperopia, with astigmatism) in persons with nondiseased eyes. The LID226397 contact lenses are a frequent replacement silicone hydrogel (SiHy) contact lenses being developed in an effort to maintain prolonged on-eye performance by utilizing an inherently wettable core lens material. These SiHy lenses have a water content of 55%, contain a UV blocker, High Energy Visible Light (HEVL) filter, and light blue handling tint. LID226397 contact lenses use the Precision Balance 8|4™ ballasted toric design concept, successfully

[figure not shown]
adopted for AIR OPTIX™ for Astigmatism. A front-curve orientation feature will consist of a fiducial mark at 6 o'clock for on-eye assessment of lens rotation.

In order for the toric contact lenses to perform effectively, they must maintain the correcting cylindrical axis in appropriate and stable orientation. Therefore, it is critical to have timely lens orientation to ideal axis, minimal lens rotation, and lens oscillation to achieve optimal performance and stable correction of astigmatism with minimal visual blur. For performance confirmation purpose, the study aims to evaluate the on-eye clinical performance of investigational LID226397 contact lenses to support contact lens product development and to evaluate product performance in the intended population. [REDACTED]

[REDACTED]

[REDACTED]

The AOfAHP contact lenses have been chosen as the comparator product because these lenses have the comparable wear modality and same indication for correction of astigmatism.

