## 7 INVESTIGATIONAL PLAN

### 7.1 Study Design

This is a prospective, randomized [REDACTED] bilateral, crossover, controlled, double-masked, multicenter clinical study, evaluating the LID226397 and AOfAHP contact lenses, to be conducted at approximately 6 sites.

Subjects will be randomized to 1 of 2 crossover sequences, [REDACTED] [REDACTED] and exposed to test and comparator lenses for bilateral wear. Subjects will be expected to complete all 7 scheduled visits. Subjects will be asked to wear their habitual spectacles only (no contact lens wear) during the washout periods for 3 to 4 days after Visit 1, and for 2 (at least 48 hours) to 4 days after Visit 4. All study contact lenses will be prescribed according to subject's prescription and fitted using the manufacturers fitting instructions. Investigator will insert the contact lenses with scribe mark in the direction of the intended 6 o'clock position (90° axis), [REDACTED] [REDACTED].

This is a double masked study design where both the investigator and the subjects will be masked to the details of the study products and assigned treatment (lens) sequences. Differences in scribe marks and lens thickness profile between the study lenses could result in potential inadvertent unmasking of investigator. [REDACTED]  
[REDACTED]  
[REDACTED]  
[REDACTED]  
[REDACTED]  
[REDACTED]

Subjects will be provided with CLEAR CARE Cleaning & Disinfecting Solution to use with the study lenses for the duration of study. LacriPure saline will be permitted for rinsing the lens(es) after removal and prior to insertion, if required.

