## 7.2 Rationale for Study Design

This study design is justified based upon an evaluation of the results of relevant preclinical and clinical testing, as described within the IB.

The investigational contact lens is intended for the optical correction of refractive ametropia (myopia or hyperopia, with astigmatism) in persons with non-diseased eyes.

The purpose of this study is to evaluate the on-eye clinical performance of investigational LID226397 contact lenses to support contact lens product development and to evaluate product performance in the intended population. [REDACTED]

The primary and [REDACTED] endpoints were selected to fulfill the primary [REDACTED] objectives of the study. Procedures for measurement of these endpoints were selected based on common practice for these assessments. The design of this study is justified based upon preclinical and clinical testing, as described within the investigator's brochure. [REDACTED]

[REDACTED] AOfAHP contact lenses were chosen as the comparator product

because these lenses also are reusable contact lenses and have the comparable wear modality and same indication for correction of astigmatism (see Package Insert for AOHP contact lenses).

The intended use of this contact lens is vision correction in astigmatism; therefore, the measurement of lens axis orientation, 10 min after insertion is planned as the primary effectiveness endpoint. [REDACTED]

The crossover design will ensure that the same subject is exposed to both the test and comparator lens materials; therefore, [REDACTED] objective assessments [REDACTED] will be obtained for both lenses from the same subject.

[REDACTED]

[REDACTED] The study will exclude any current/habitual AOfAHP lens and daily disposable contact lens wearers, and any previous wearers of AOfAHP or daily disposable contact lenses in the past 3 months prior to consent in order to reduce potential bias of wearers to their habitual contact lenses. There are no immediate plans to submit the results of this pivotal study for publication; however, the results may be offered for publication if they are of scientific interest, or if the results relate to a product that is subsequently approved or cleared for marketing.

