## 8.1 Inclusion Criteria

Written informed consent must be obtained before any study specific assessment is performed. Upon signing informed consent, the subject is considered enrolled in the study.

Subjects eligible for inclusion in this study must fulfill **all** of the following criteria:

1. Subject must be at least 18 years of age.
2. Subject must be able to understand and must sign an informed consent form (ICF) that has been approved by an Institutional Review Board (IRB/IEC).
3. Successful wearers of any commercial toric soft contact lenses (except AOfAHP and daily disposable lenses) in both eyes with at least 3 months wearing experience, with a minimum wearing time of 5 days per week and 10 hours per day.
4. BCVA distance (as determined by manifest refraction at screening) 20/25 or better in each eye with a sphero-cylindrical refractive error within the available study lens parameter range in the study.

Note: Study lens parameters available in this study are:

-0.75 D and -1.25 D cylinder power with:

- (a) -0.25 to -4.00 D (in 0.25 D steps) spherical power in 10°, 90°, 170° and 180° axis as available
- (b) -5.00 to -10.00 D (in 1 D steps), -5.50 D & -6.50 D spherical power in 90° and 180° axis as available
- (c) +1.00 to +8.00 D (in 1 D steps) spherical power 90° and 180° axis as available

5. Distortion-free keratometric readings at screening

6. Subject must possess spectacles (with 0.3 logMAR or better vision OU) and be willing to wear habitual spectacles for vision correction when study lenses are not worn, as needed.
7. Subject must be willing to stop wearing their habitual contact lenses for the duration of study participation.

9. Willing to NOT use rewetting/lubricating drops at any time during the study.
10. Subjects must be willing and able to attend all scheduled visits.

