
Product description and parameters available for this study
	
 
• Material: Serafilcon A
 
• Water content: 55%
 
 
Power range: Limited lens parameters will be available for use in this study:
 
 
• -0.75 D cylinder power with             
 
(a) -0.25 to -4.00 D (in 0.25 D steps) spherical power in 10°, 90°, 170° and 180° axis as available
 
(b) -5.00 to -10.00 D (in 1 D steps), -5.50 D & -6.50 D spherical power 90° and 180° axis as available
 
(c) +1.00 to +8.00 D (in 1 D steps) spherical power 90° and 180° axis as available
 
 
 
• -1.25 D cylinder power with             
 
a) -0.25 to -4.00 D (in 0.25 D steps) spherical power in 10°, 90°, 170° and 180° axis as available
 
b) -5.00 to -10.00 D (in 1 D steps), -5.50 & -6.50 D spherical power 90° and 180° axis as available
 
c) +1.00 to +8.00 D (in 1 D steps) spherical power 90° and 180° axis as available
 
 
 
• Base curve (mm): 8.6 mm (Target)
 
• Diameter (mm): 14.5 mm (Target)
 

Formulation
	
Details are present in the IB for CLN109-C001 V3.0

Usage
	
 
• Wear:             
 
○ Daily Wear
 
 
 

	

○ Bilateral

 

 

• Replacement lenses will not be provided to the subject. In the event a lens needs to be replaced, the subject must return to the site for a replacement lens. Until the replacement lens is obtained, the subject must store both study lenses in the provided lens care solution and wear their habitual spectacles.

• Exposure: Study lenses are to be worn during typical contact lens wearing hours, on all days during the study lens wearing period, at least 10 hours per day, over each treatment period (7 days [-0/+1] according to randomization assignment). 

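### Does the ±30° band make the primary endpoint too wide to show how well the test lens orients?

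*SAP*

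**What the plan says.** SAP 4.1 defines the primary endpoint as the percentage of test lenses with "axis orientation, recorded as deviations from 90° axis, between -30 degrees and +30 degrees, inclusive". There is a single reading, taken ten minutes after the lens goes in, when it is dispensed. Protocol 12.4.1 says the same, and the primary objective (protocol 6.1, SAP 1.1) is to evaluate this same percentage. Protocol 12.4.1.1 and SAP 4.2 state that no inference is made and no hypothesis is set. The SAP's executive summary declares success criteria not applicable.

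Protocol 7.2 explains why orientation was chosen: the lens corrects astigmatism, so "the measurement of lens axis orientation, 10 min after insertion is planned as the primary effectiveness endpoint". The visible text gives no reason for the figure of 30°, but a redaction follows directly.

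The assessments in the protocol summary record orientation in degrees of deviation from the 90° axis. SAP section 4 gives mean, SD, median, minimum and maximum for continuous variables and plans a listing of selected effectiveness data. SAP 4.3.1 and protocol 12.4.1.2 begin by promising frequencies and percentages, and then the sentence is blacked out.

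**The concern.** Protocol 5.1 says that for a toric lens "it is critical to have timely lens orientation to ideal axis, minimal lens rotation, and lens oscillation to achieve optimal performance". Set beside that, a band of 30° either way looks very wide. At its edge a matched cylinder leaves as much astigmatism, in magnitude, as no cylinder correction at all.

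Two features of the design seem to make this worse. Lenses are stocked with "spherical power in 10°, 90°, 170° and 180° axis as available" for the lower minus powers and in 90° and 180° only for the others, so rotation seems hard to offset by choosing another axis. And the protocol says "Investigator will insert the contact lenses with scribe mark in the direction of the intended 6" o'clock position, so the lens seems to start aligned.

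If all this held, a percentage close to 100% would fit both a well-aligned lens and one that rotates systematically by 20° to 25°. The headline result would then say little about the performance that the study is meant to confirm.

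**Working it through.** The plan gives no expected percentage and no rotation distribution, so there is no figure of its own to reproduce.

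**1. Optics.** The inputs are the two cylinder powers in protocol 8.1 ("0.75 D and -1.25 D cylinder power with" the stated sphere ranges) and the 30° limit. For lens cylinder C equal to the eye's cylinder and rotation t, the residual is 2C·sin(t).

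| Rotation | 2·sin(t) | C = 0.75 D | C = 1.25 D |
|---|---|---|---|
| 10° | 0.347 | 0.26 D | 0.43 D |
| 20° | 0.684 | 0.51 D | 0.86 D |
| 25° | 0.845 | 0.63 D | 1.06 D |
| 30° | 1.000 | 0.75 D | 1.25 D |

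If the eye's cylinder E differs from C, the residual at 30° is √(E² + C² − 2EC·cos 60°):
- E = 1.00, C = 0.75: √0.8125 = 0.90 D, or 90% of E.
- E = 1.50, C = 1.25: √1.9375 = 1.39 D, or 93% of E.
- E = 1.00, C = 1.25: √1.3125 = 1.15 D, or 115% of E.

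So the optical statement is right at the edge of the band, and exact when the cylinders match. It describes the worst lens counted, not the typical one.

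**2. Would a systematic rotation stay hidden?** Assume normal rotation with mean m and SD s. The share within ±30° is Φ((30 − m)/s) − Φ((−30 − m)/s). The second term is negligible in the last four rows.

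| Mean | SD | Within ±30° |
|---|---|---|
| 0° | 5° | 100.0% |
| 0° | 10° | 99.7% |
| 20° | 5° | Φ(2.0) = 97.7% |
| 20° | 10° | Φ(1.0) = 84.1% |
| 25° | 5° | Φ(1.0) = 84.1% |
| 25° | 10° | Φ(0.5) = 69.1% |

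In three of the four shifted cases the endpoint falls by 15 percentage points or more. Only a 20° shift with a tight spread stays close to the ceiling.

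**3. Axes.** Axis is circular modulo 180°, so 170°, 180° and 10° are neighbours and the step from 170° to 10° is 20°. A general limit of 10° on any shift is therefore wrong; it holds for a lens at 180°. Lenses at 90°, and powers stocked only at 90° and 180°, do have no close neighbour.

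**4. Insertion.** The sentence in protocol 7.1 is redacted immediately after the axis. What the investigator does next is not visible, so the 10-minute reading cannot be described as merely asking whether an aligned lens stays put.

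**5. Is anything finer missing?** The visible text does not allow that conclusion:
- The analysis sentence for the primary endpoint is cut off by redaction in both documents.
- Protocol 7.2 and 7.3 have a blacked-out term between the word primary and the word endpoints.
- The protocol contents have a redacted entry between 6.2 and 6.4, and Table 6-1 is followed by Table 6-3.
- The axis-orientation row in both schedules has blacked-out text before the 10-minute time point.
- The visible SAP headings jump from 4.3.1 to 4.6.

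Text removed by redaction is not text missing from the plan.

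**The case for a change.** The strongest reply is that the ±30° percentage discriminates poorly and that the visible text commits to nothing finer. With mean rotation 0° and an assumed SD rising from 5° to 15°, the share within ±30° moves only from 100% to 95.4%, while the share within ±10° falls from 95.4% to 49.5%. With a mean of 20° and SD 5°, 97.7% still lie within ±30°. For 80 completers with two lenses each, that is about 156 of 160 lenses (0.977 × 160), against 160 of 160 for a centred lens. Within ±10° the figures would be 2.3% and 95.4%. The general rule for continuous variables does not name orientation, and the endpoint itself is a percentage.

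Part of this stands. The ±30° figure taken alone is a coarse measure, and the visible text does not say why 30° was chosen. But these are assumed distributions, chosen where the band is least sensitive. A low percentage would still be informative. The proposed additions would leave the endpoint as it is and put more descriptive bands beside it. Of those, ±10° is a stocking step for a deliberately limited set of study lenses, not a performance limit, and ±20° has no source in the documents.

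**Conclusion.** The concern does not hold. Endpoint and primary objective are the same quantity, and the result is descriptive, with no success rule that a lenient band could help to meet. The optical calculation is correct but applies to the edge of the band: 100% residual for matched cylinders, 90% to 115% in the unmatched examples. A systematic rotation of 20° to 25° would give between 97.7% and 69.1% within ±30°, assuming normal rotation and an SD of 5° to 10°, so it would usually be seen. Whether tighter bands or summaries in degrees are planned cannot be judged from the redacted text. The data are recorded in degrees, and the SAP has a rule for summarising continuous variables. What remains is a preference for more descriptive detail, not an error in the plan.

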4.2 Effectiveness Hypotheses

Primary Effectiveness

No inferences are to be made on the primary effectiveness endpoint; therefore, no hypotheses are formulated.

[figure not shown]

[figure not shown]

[figure not shown]
4.3 Statistical Methods for Effectiveness Analyses

[figure not shown]
4.3.1 Primary Effectiveness Analyses

[figure not shown]
Frequencies and percentages will be provided, [REDACTED]
[REDACTED]
[REDACTED]

[figure not shown]

4.6 Interim Analysis for Effectiveness

No interim analysis is planned for effectiveness endpoints.

5 SAFETY ANALYSIS STRATEGY

The focus of the safety analysis will be a comprehensive descriptive assessment of occurrence of adverse events as well as the other listed parameters. Therefore, no inferential testing will be carried out on the safety data.

5.1 Safety Endpoints

The safety endpoints are

- AEs

- Biomicroscopy Findings
 - Limbal hyperemia
 - Bulbar hyperemia
 - Corneal staining
 - Conjunctival staining
 - Palpebral conjunctival observations
 - Corneal epithelial edema
 - Corneal stromal edema
 - Corneal vascularization
 - Conjunctival compression/indentation
 - Chemosis
 - Corneal infiltrates
 - Other findings
- Device deficiencies

5.2 Safety Hypotheses

There are no formal safety hypotheses in this study. The focus of the safety analysis will be a comprehensive descriptive assessment of safety endpoints listed in Section 5.1.

